9 STUDY PROCEDURES

Detailed descriptions of subject evaluations required for this protocol are described in this section. These evaluations will be performed during the indicated visits/weeks of the study as described in the Study Calendar and in this section.

All data collected are to be recorded on source documents and entered into the appropriate CRF page.

The PI is responsible for maintaining a record of all subjects pre-screened, screened, and enrolled into the study. All subjects must provide written informed consent before the performance of any study procedures.

9.1 Informed Consent

Prior to conducting any study-related procedures, written informed consent will be obtained from the subject. The nature, scope and possible consequences, including risks and benefits, of the study will be explained to the subject by the PI or designee in accordance with the regulations and guidelines in the Statement of Compliance.

9.2 Study Entrance Criteria

At screening, each subject will be assessed for eligibility against the inclusion/exclusion criteria. Subjects who do not meet the study entrance criteria will not be allowed to enroll and participate in the study. The reason(s) for ineligibility will be documented in the subject research chart.

9.3 Demographics, Medical History and Hypoglycemia Awareness Survey

Subject information including gender, age, date of birth, race, ethnicity, diagnosis of (condition), and other relevant past medical history will be collected during the screening period and recorded in the appropriate CRF. Subjects will also be administered a questionnaire to evaluate hypoglycemia awareness.

9.4 Laboratory Variables

A 30mL blood draw will be conducted to obtain blood samples for routine and safety clinical laboratory tests (hematology, clinical chemistry) as indicated below. In addition, participants will be asked to leave a 100-120mL sample of urine for urinalysis and pregnancy testing as indicated below. Analysis of laboratory samples will be performed by ARUP Laboratories: [name].

9.4.1 Hematology and Clinical Chemistries

Hematology: hematocrit, platelet count, white blood cell count, hemoglobin

Serum Chemistries and Liver Function Tests: potassium, sodium, blood urea nitrogen, albumin, alkaline phosphatase, aspartate aminotransferase, alanine aminotransferase, total bilirubin, creatinine,

Additional tests: TSH, glucose levels, C-peptide, HbA1c

9.4.2 Urinalysis

Urinalysis will be performed to evaluate urine microalbumin levels.

9.4.3 Pregnancy Testing

A urinary pregnancy test evaluating human chorionic gonadotropin (hCG) levels will be performed during the initial screening visit, at the time CGM is placed, as well as the night before each of the hypoglycemic clamp studies.

9.4.4 Specimen Collection, Preparation, Storage and Shipping

The collection, preparation, storage and shipping of specimens will be conducted in accordance with procedures outlined by ARUP Laboratories. Blood samples collected for assessment of plasma glucose during the clamping procedure will be collected into heparin coated tubes to prevent coagulation.

9.5 Physical Examination

A complete physical examination including assessment of the respiratory system, cardiovascular system, abdomen as well as specific tests for neuropathy will be conducted at the screening visit.

9.6 Vital Signs

Vital signs, including measurement of systolic and diastolic blood pressure, pulse, heart rate, respiration rate and O₂ saturation will be measured at the screening visit, as well as during the hypoglycemic clamp sessions.

9.7 Electrocardiogram

An ECG will be completed during the screening period to assess for cardiac conduction abnormalities.

9.8 Continuous Glucose Monitor (CGM) and Glucometer

A blinded continuous glucose monitor (CGM) will be placed after enrollment and continue until the end of the second hypoglycemic clamp study. At this time, the participants will also be issued a Bayer Contour Next EZ[®] glucometer which they will use to monitor their blood glucose for the duration of the study and also to calibrate the CGMs. Instructions on how to use the glucometer will be provided at this time.

9.9 Concurrent Medications

All prescription and non-prescription medications including pharmacologic doses of vitamins, herbal medicines, or other non-traditional medicines, taken from 5 weeks prior to the first dose of carvedilol through the last study visit must be documented and recorded in the CRF.

9.9.1 Prohibited Concurrent Medications

The following medications are prohibited during the study:

- Use of any other beta blocker
- Use of diuretics
- Use of benzodiazepines
- Use of acetaminophen
- Use of SSRIs, naltrexone and other medications that have been proposed to have the potential to improve hypoglycemia awareness or prevent the development of impaired awareness of hypoglycemia.

9.10 The Clamp Procedure

Patients will be asked to reduce the dose of long-acting insulin 24 hours prior to the clamp study if applicable. The night before the clamp study, the subjects will be admitted into the CSC and the CGMs will be checked for hypoglycemia (reading <75-80mg/dl). We are setting this cut-off a little higher than the clinical definition of hypoglycemia (<70mg/dL) to ensure central mechanisms that are normally triggered by mild hypoglycemia are not activated⁷⁵. If hypoglycemia (<75-80mg/dL) is noted within 24 hours of beginning the clamp study, then the study will be delayed for one week. Qualifying subjects will be provided with a standardized low glycemic index meal to avoid fluctuations in blood glucose levels during the overnight fast. The CSC nursing staff will introduce an intravenous (antecubital vein) insulin drip in the subject and blood glucose levels will be maintained between 90-120mg/dl during the overnight fasting period. Blood glucose concentrations will be determined from a fingerstick using a point-of-care glucometer in order to titrate the insulin drip.

First Hypoglycemic Clamp: The next day, the patient will be asked to void their bladder prior to the start of the clamping procedure. The participant will then remain in bed in a supine position for the procedure. The participant will be asked to refrain from watching television during the procedure. A second catheter will be inserted into the contralateral hand vein for blood sampling and the sampling hand placed into a heated (~55°C) box to arterialize the blood. An ECG will also be connected to the subject to monitor heart electrical activity. Heart rate, blood pressure and ECG will be monitored every 15 minutes throughout the study. Prior to the drawing of each blood sample, the deadspace volume (~5-6ml) will be withdrawn into a syringe. A new syringe will be replaced onto the luer lock and the required blood volume drawn into new syringe. Following blood collection, the collected deadspace volume will be reinfused, followed by a saline infusion through the intravenous line to clear it of residual blood. Baseline blood samples (30mL) will be

collected to measure glucose, HbA1c, hematocrit and hormones (glucagon, catecholamines, insulin, cortisol, growth hormone, pancreatic polypeptide). Blood samples collected for assessment of plasma glucose (1mL) during the clamping procedure will be aliquoted into heparin coated 1ml Eppendorf tubes to prevent coagulation and processed immediately in the YSI and/or Analox Instruments glucose analyzer. In addition, the participants will be asked to fill in questionnaires to assess their perception of hypoglycemic symptoms (Edinburgh Hypoglycemia Symptom Scale) and their fear of hypoglycemia. Subsequently, the subjects will be given KCl tablets (20-40mEq) to help maintain potassium levels during the clamping procedure. Once assessment of baseline parameters has been completed, constant insulin (2mU/kg/min) and variable 20% dextrose infusions will be started at -60 minutes to establish stable glucose levels of ~90mg/dl before gradually lowering plasma glucose levels in three steps from 90-65-55-45 mg/dl by gradually reducing the glucose infusion rate. Plasma glucose levels will be monitored from a 1ml blood sample every 5min using a YSI and/or Analox glucose analyzer. A second Analox Instruments glucose analyzer and glucometer will be kept on hand as a backup. It is important that the glucose levels NOT be communicated verbally during the clamping procedure as notification of declining glucose concentrations to the participant might trigger confounding (i.e. artificially higher) awareness scores or stress hormone responses. Each glycemic step will be held for 30 minutes, allowing enough time for blood collection (~30mL at each glycemic plateau) and completion of the Edinburgh questionnaire at each glycemic plateau. At each glycemic step, plasma hormones (glucagon, catecholamines, insulin, cortisol, growth hormone, pancreatic polypeptide) will be evaluated. The frequent assessment of hypoglycemia symptom scores allows us to identify the threshold at which hypoglycemic symptoms are first noticed by the subject. We chose glycemic targets of 55 and 45mg/dl as hypoglycemic symptoms generally first appear between 55-65mg/dl in hypoglycemia aware individuals. In contrast, symptoms may not manifest in hypoglycemia unaware patients until glucose levels reach 45mg/dl. Targets of 55 and 45mg/dl allow us to safely determine whether carvedilol treatment raises the glucose threshold at which symptoms are first detected (i.e. improving hypoglycemia awareness). No more than 500mL of blood will be collected throughout the entire clamping procedure which is equivalent to the volume of a single blood donation. After the clamp, the participant's glucose levels will be recovered to normal by stopping the insulin infusion and raising the glucose infusion rate. In addition, a meal will be provided to aid recovery. This first set of clamps will establish a baseline response in the participant prior to the start of the intervention phase of the study. **Dispersal of Intervention Drug:** At the end of the clamp procedure, the subjects will be supplied with either placebo or one of two different doses of carvedilol, 2.5mg or 3.125mg, along with instructions on how to take the medication. The research staff and participant will be blinded to the treatment being received. The initial dose will be taken on the day following the clamp. In addition, the participant will also receive a hypoglycemia log book along with instructions on how to document hypoglycemia incidences and whom to contact in case of medical concerns. Once the participant's blood glucose levels are stable and he/she is ready to be discharged, we will provide them with glucose tablets and we will cover the cost of transportation home as a precautionary measure.

Follow-Up Visit: About 7-14 days after the start of the intervention phase, the subjects will be asked to come into the clinic for a follow-up visit where vital signs, AE and CGM data will be monitored or evaluated. Subjects will also be asked to complete a hypoglycemia awareness and fear survey at this time.

Second Hypoglycemic Clamp: At the end of the four-week intervention phase, the subjects will return to the CSC for the overnight stay and second hypoglycemic clamp procedure. The second hypoglycemic clamp procedure will be identical to the first described above.

9.11 Efficacy Measurements

On all treatment visit days, dosing will occur after all of the safety and efficacy assessments that are scheduled for that particular visit have been completed.

9.11.1 Primary Objective Assessment

The primary objective assessments are 1) improvements in the hypoglycemia symptom scores at each of the (hypoglycemic) glycemic plateaus, 2) shift in the threshold for the detection of hypoglycemia and 3) whether counterregulatory hormone responses improve during the second hypoglycemic clamp in T1DM patients with impaired awareness of hypoglycemia after 4 weeks of carvedilol treatment compared to their baseline and/or compared to the placebo-treated control group.

The symptom scores will be assessed by the Edinburgh Hypoglycemia Symptom Score. Results will be kept in the patients CRF. After the study is complete, the results will be loaded into a secure electronic database and analysis will begin. When reporting the results of the hypoglycemia symptom scores, we will evaluate individual as well as overall or total symptom scores. In addition, symptoms will be grouped into autonomous, neuroglycopenic and other symptoms for evaluation.

The counterregulatory hormone responses (glucagon, epinephrine, norepinephrine, cortisol and growth hormone) will be analyzed from the drawn blood samples. Whole blood samples will be collected and aliquoted into vacutainers containing the appropriate preservatives and anticoagulants, spun down and the plasma portion will be stored in a -80°C freezer until the samples are analyzed.

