Study Product, Dose, Route, Regimen	Hypoglycemia unaware T1DM subjects will be randomly segregated into one of two therapeutic treatment groups: Placebo or Carvedilol. Carvedilol will be administered orally at either 2.5mg or 3.125mg twice daily. Likewise, the placebo drug will also be administered orally twice daily.
Duration of Administration	4 weeks
Reference Therapy	Placebo
Statistical Methodology	Treatment effects will be analyzed using one- or two-way analysis of variance (ANOVA) for independent or repeated measures as appropriate, followed by suitable post-hoc analysis. Analyses will be performed using the GraphPad Prism® or SAS® suite of software.

STUDY SCHEMA

[figure not shown]

Figure 1: Schematic of the study design.

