1. OBJECTIVES

1.1 Primary Objectives and Endpoints

- To investigate whether T1DM patients with impaired awareness of hypoglycemia receiving carvedilol treatment will show marked improvements in hypoglycemia symptomatic awareness scores, as well as improvements in their counterregulatory hormone responses to hypoglycemia.

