4 STUDY DESIGN

4.1 Description

The current study will be a double-blinded, placebo-controlled study in which Type 1 diabetic patients with hypoglycemia unawareness are randomized to either 1) placebo treatment, 2) 2.5mg carvedilol twice daily or 3) 3.125mg carvedilol twice daily. After enrollment, the participants will be placed on (blinded) CGM monitoring which will be continued until the end of the study. Additionally, participants will be provided with a glucometer to measure their blood glucose and for calibrating the CGMs during the study. One week after CGM placement, the participants will undergo the first hypoglycemic clamp study to obtain baseline measures of hypoglycemia frequency (from downloaded CGM data), hypoglycemia awareness scores and hormone responses. Following the initial clamp procedure, the patients will be randomized to either 4 weeks use of carvedilol or placebo. After the 4 weeks of treatment, the participants will undergo a second hypoglycemic clamp session. Patients will be hospitalized the night before each clamp study to ensure stable glucose levels.

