9.11.2 Secondary Objective Assessment

The secondary objective assessment will establish whether the frequency of CGM-determined hypoglycemic episodes differs during 4 weeks of carvedilol treatment compared to baseline and compared to the placebo-treated control group.

Patients will wear a blinded CGM that is installed 14 days prior the first clamp study and the device will continue to be worn throughout the entire study. These CGMs will be calibrated using the provided Bayer Contour Next EZ[®] glucometer. During the first clamp study, the follow-up visit and the second clamp study, data from the CGM will be downloaded and saved onto a secure server and exported into an Excel format for analysis. We will identify the number hypoglycemic excursions during the intervention period and compare this to the number of hypoglycemic episodes encountered during the 7-day period before the first clamp study, the “baseline” period. Comparisons between treatment groups at baseline and following the intervention period, as well as differences from baseline within each treatment group will be made.

Analysis of the CGM data will emphasize the number of hypoglycemic episodes as well as the duration and depth of the hypoglycemic episodes. A single hypoglycemic episode is defined as a glucose reading <70 mg/dL, followed by a reading ≥ 70 mg/dL, lasting at least 15 minutes or at least two readings below 70mg/dL over 15 minutes. If there is less than 30 minutes between two registered episodes of hypoglycemia these are considered as one episode.

We will also evaluate the answers to the fear surveys to determine whether those patients who are treated with carvedilol have a reduction in their fear of hypoglycemia compared to those on placebo.

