10 STATISTICAL CONSIDERATIONS

A total of 21 T1DM patients with impaired awareness of hypoglycemia will be sought for this study. For the dose response study, we plan to enroll 21 of these patients who will be randomized to either placebo (N=7) or carvedilol (2.5mg or 3.125mg twice daily; N=7 each).

In estimating the appropriate sample sizes required to yield adequate statistical power, assuming a Type II error rate (β) of no more than 20% for a given test and a Type I error rate of $\alpha=5\%$, we used the following: $\text{Power} \geq 1-\beta = 1-0.2 = 0.8$

Treatment effects will be analyzed using one- or two-way analysis of variance (ANOVA) for independent or repeated measures as appropriate, followed by suitable *post-hoc* analysis. Analyses will be performed using the GraphPad Prism[®] or SAS[®] suite of software. We will use a significance level of $\alpha<0.05$.

Primary variables:

- a) Symptom Scores (autonomous, neuroglycopenic and other symptoms of hypoglycemia)
- b) Counterregulatory Hormone Responses (glucagon, epinephrine, norepinephrine, growth hormone and cortisol levels)

Secondary variables:

- a) Frequency of hypoglycemia assessed by CGM.

The primary and secondary variables will be analyzed by the statistical approaches mentioned above.

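### Section 9.11.1 lets the primary assessments be judged against baseline alone, and nothing in the plan makes the placebo comparison decide

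*Combined protocol and SAP*

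**What the plan says.** Section 9.11.1 lists three primary assessments: symptom scores at the hypoglycemic plateaus, the threshold for detecting hypoglycemia, and the counterregulatory hormone responses. It says improvement will be judged "compared to their baseline and/or compared to the placebo-treated control group".

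The other relevant places are these:

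- **Section 4.1 (design):** "The current study will be a double-blinded, placebo-controlled study in which Type 1 diabetic patients with hypoglycemia unawareness are randomized" to placebo or one of two carvedilol doses. The Study Summary names placebo as the reference therapy.
- **Section 1.1 (primary objective):** patients "receiving carvedilol treatment will show marked improvements in hypoglycemia symptomatic awareness scores". No comparator is named.
- **Section 10 (analysis):** "Treatment effects will be analyzed using one- or two-way analysis of variance (ANOVA) for independent or repeated measures as appropriate", followed by post-hoc tests that are not specified. No model term, contrast or success rule is given.
- **Section 9.11.2 (secondary):** hypoglycemia frequency on CGM is compared with baseline and with placebo. Comparisons between groups are planned, "as well as differences from baseline within each treatment group will be made". The fear survey is compared with placebo only.

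**The concern.** Randomization and blinding protect the comparison between arms. They do not protect a comparison of an arm with its own baseline. Read literally, the *or* in section 9.11.1 allows a within-arm change in a carvedilol group to count, and any favourable change that placebo patients also show would then be credited to the drug.

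Several things start or recur in every arm after the first clamp. The clamp is repeated ("The second hypoglycemic clamp procedure will be identical to the first described above"), patients keep a hypoglycemia log book, and they attend a follow-up visit with awareness and fear surveys. These could move self-reported symptom scores; they would not directly move assayed hormones. A common change could also be unfavourable, since section 2 explains that recent hypoglycemia blunts later responses. What is at stake is a report of improved awareness or hormone response when placebo improved equally.

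**Working it through.** **Text.** Section 9.11.1 joins the two comparators without ranking them, and section 1.1 names none. Section 10 would be satisfied by a two-way repeated-measures model with a group-by-clamp term. It would equally be satisfied by a one-way repeated-measures analysis inside a carvedilol arm. Section 9.11.2 is firmer, but covers secondary outcomes only. No passage closes the gap.

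**Inputs.** There are 7 patients per arm in three arms (sections 4.3 and 10), with alpha 5% and power of at least 80% (section 10). Sidedness is not stated; two-sided is assumed. No effect size or SD is given, so N = 21 cannot be reproduced, and everything below is in SDs of the change score. No success rule is given either. The rule assumed is that either comparison, favourable for at least one dose, suffices.

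**Within-arm test.** t = mean change / (s/√7), 6 df, critical value 2.447. Under a common shift δ the noncentrality is δ√7. At δ = 0.25 this is 0.66, giving 8.1% for one arm and 1 − (1 − 0.081)² ≈ 16% for either dose.

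**Placebo contrast.** t = (carvedilol mean change − placebo mean change) / (s√(2/7)), 12 df, critical value 2.179. The shift δ cancels, leaving about 2.5% per dose and about 4.6% for either dose.

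**False-positive rate with no drug effect.** Simulation, one endpoint, normal change scores. The adjusted columns use pooled variance on 18 df, Šidák over three arms for the within-arm tests, and Dunnett (2.40) for the placebo contrasts.

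| Common shift (SD) | And/or, unadjusted | Placebo contrasts, unadjusted | Positive on baseline only, unadjusted | And/or, adjusted | Placebo contrasts, adjusted |
|---|---|---|---|---|---|
| −0.5 | 4.6% | 4.6% | 0.1% | 2.5% | 2.5% |
| −0.25 | 5.1% | 4.6% | 0.6% | 2.6% | 2.5% |
| 0 | 7.9% | 4.6% | 3.3% | 3.5% | 2.5% |
| 0.1 | 10.5% | 4.6% | 6.0% | 4.6% | 2.5% |
| 0.25 | 17.2% | 4.6% | 12.6% | 8.2% | 2.5% |
| 0.5 | 36.6% | 4.6% | 32.0% | 22.6% | 2.5% |

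**Power, true benefit of 1.0 SD in both doses, unadjusted, at least one dose positive.** With no common shift, the and/or rule gives 87% and the placebo contrasts 57% (46% with Dunnett on change scores). With a shift of −0.5 SD, the figures are 63% and 57%.

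**Effect needed for 80% power per dose, 7 per arm.**

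- Paired test within an arm: 1.27 SD.
- Two-sample t-test on change: 1.63 SD.
- ANCOVA on the first-clamp value: with equal variances at both clamps and baseline correlation r, the residual SD is √((1 + r)/2), which is 0.81, 0.87 and 0.92 at r = 0.3, 0.5 and 0.7. With 17 error df and chance baseline imbalance included, the effects are 1.32, 1.42 and 1.51 SD unadjusted, and 1.46, 1.57 and 1.67 SD with Dunnett (2.41).

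**The case against.** The strongest reply is that section 9.11.1 lists what will be assessed and sets no success rule, so its wording may only mean that both comparisons will be examined. The design points the same way: placebo is the reference therapy, section 10 speaks of treatment effects, and a two-way repeated-measures ANOVA would normally carry a group-by-clamp term. This makes a before-after conclusion less likely but does not exclude it. The stricter wording for the secondary outcomes does not extend to the primary ones.

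The second reply is that the harm needs a favourable common shift that no document supports, and that the only mechanism the background describes runs the other way. That stands as a limit on size. At −0.5 SD there is no inflation, and at zero shift with adjusted tests the difference is 3.5% against 2.5%. The 37% figure needs a 0.5 SD shift, unadjusted tests and the assumed success rule.

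The third reply is that relying on placebo costs power: 57% against 87% at zero shift for a 1.0 SD benefit. That is true and should be acknowledged, but the extra power comes from a comparison that cannot separate drug effect from shared change.

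Finally, naming the placebo contrast would cure the defect by itself; ANCOVA with Dunnett is a recommended way of doing so, not the only one.

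**Conclusion.** The concern holds and should be fixed. The plan does not say which comparison decides the primary conclusion, and its wording permits a before-after change alone. That finding about the text is firm.

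The size is conditional. Unadjusted, the and/or rule roughly doubles the false-positive rate with no common shift (about 8% against 4.6%), and raises it to 17% and 37% at favourable shifts of 0.25 and 0.5 SD. Under an unfavourable shift there is little or no inflation. These figures rest on an assumed shift, an assumed rule that either comparison suffices, two-sided tests, normal change scores and a single endpoint. Multiplicity across the listed variables and plateaus is a separate matter and is not included.

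**What to change.** In sections 9.11.1 and 10, replace the and/or wording with one deciding type of comparison: each carvedilol dose versus placebo at the second clamp, by ANCOVA adjusted for the first-clamp value, with a Dunnett adjustment for the two doses. Apply it to symptom scores and hormones at each hypoglycemic plateau. Dose-specific treatment-by-clamp contrasts are an acceptable alternative. The omnibus two-degree-of-freedom interaction is not, because it does not say which dose differs from placebo.

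The detection threshold is observed only at a few glucose steps ("gradually lowering plasma glucose levels in three steps from 90-65-55-45 mg/dl") and may not be reached. Compare each dose with placebo there too, using a method for ordered or censored data, for example an exact rank test with non-detection by the last step as the lowest category. State how the two doses and the first-clamp value are handled in that test.

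State that within-arm changes from baseline are descriptive and do not by themselves support the primary conclusion.

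The change is to wording only; all the data are already collected. The cost is sensitivity. The effect needed for 80% power per dose rises from 1.27 SD for a before-after test to between 1.46 and 1.67 SD for the recommended analysis, at assumed baseline correlations of 0.3 to 0.7.
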